T2: Exit Survey

- Acceptability and implementation measures for the MyVoice tool
- Reproductive knowledge (ReproKnow)
- Self-efficacy (Perceived Efficacy in Patient-Provider Interactions [PEPPI])
- Decision Conflict Scale (Low Literacy version)
- Interpersonal Quality of Family Planning (IQFP) Scale

T3: Provider Survey

- Providers' experiences with the study as well as information related to encounters with patients enrolled in the study

T4: 3 Month Survey

- National Survey of Family Growth Family Planning Services Question
- Self-efficacy (Perceived Efficacy in Patient-Provider Interactions [PEPPI])
- Reproductive knowledge (ReproKnow)
- London Measure of Unintended Pregnancy

D. Risk/Benefit Assessment

Known Potential Risks

- Discomfort- Study activities involve information regarding reproductive health; some individuals may be uncomfortable discussing this topic.
- Invasion of Privacy- Participants may feel uncomfortable discussing their reproductive health where other individuals may hear them.
- Breach of Confidentiality- Any possibility that de-identified information could be viewed by unauthorized parties.

Known Potential Benefits

- This pilot study will inform the procedures and practices related to a future full-scale testing of a patient-facing decision support tool for family planning. Our study team and others have demonstrated that women with rheumatic diseases do not receive adequate family planning care. We will not directly counsel patients about their particular risks, and therefore, patients will not receive a direct benefit from their participation. However, they may learn more about their family planning options in the context of their diseases.

Assessment of Potential Risks and Benefits

- Discomfort- We will minimize occurrence of discomfort by being clear about the content of the study tool and assessment measures during recruitment. All questions in study surveys and interviews will be optional, and participants will be told they can skip any question they do not wish to answer.
- Invasion of Privacy- The study will not be discussed with potential or current participants in public settings. Conversations about the study will only occur in private exam rooms or research spaces or via email or phone conversations. We will minimize risk by placing phone calls while in a private room and asking the potential participant whether they are in a private location before discussing the study.

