Ideally, the exit survey and interview will be completed immediately after the patient leaves her rheumatologist visit. However, if participants are unable to complete the study activities at that time, research coordinators will schedule a time to complete them over the phone between 24-48 hours after the visit.

Research coordinators will collect the following PHI from electronic health records of participants within 24 hours of their rheumatology visit, and again 90 days later at T4:

- Orders for pregnancy tests (urine, serum)
- Orders for emergency contraception
- Billing code for family planning or contraception counseling
- Order for non-emergency contraception method
- Order/Referral for obstetrics-gynecology or maternal-fetal medicine consultation
- Order/Referral for PCP consultation for family planning indication
- Prescription for prenatal vitamin
- Change from fetotoxic/teratogenic disease-modifying anti-rheumatic drug or small molecule medication to a pregnancy-compatible anti-rheumatic drug
- Documentation of pregnancy

G2e. T3: 2 Weeks Post-Recruitment Completion (Providers)

T3 is a time point only relevant to rheumatology providers. No action is needed from participants at T3.

The following forms will be completed at T3:

- Provider Survey: This survey will be given to rheumatology providers with one or more patients enrolled in the research study. This survey asks providers about their

experience with the study as well as information related to encounters with patients enrolled in the study.

Providers will be emailed this survey to complete through a REDCap link. Emails with the REDCap link to the survey will be sent out 2 weeks after our final participant completes their T2 survey. Providers will **NOT** be informed of which of their patients participated in the study. Study personnel will follow up with providers once a week via email to complete the survey a maximum of three times.

G2f. T4: 3 Months Post-Intervention

T4 will begin for participants 3 months post-intervention.

The following forms will be completed at T4:

- 3 Month Survey: This survey asks participants about any potential pregnancies post-intervention, their current birth control habits, and their knowledge on pregnancy risks in the context of rheumatic disease.

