Research coordinators will collect the following PHI from electronic health records of participants within 24 hours of their rheumatology visit, and again 90 days later at T4:

- Orders for pregnancy tests (urine, serum)
- Orders for emergency contraception
- Billing code for family planning or contraception counseling
- Order for non-emergency contraception method
- Order/Referral for obstetrics-gynecology or maternal-fetal medicine consultation
- Order/Referral for PCP consultation for family planning indication
- Prescription for prenatal vitamin
- Change from fetotoxic/teratogenic disease-modifying anti-rheumatic drug or small molecule medication to a pregnancy-compatible anti-rheumatic drug
- Documentation of pregnancy

G3e. T3: 2 Weeks Post-Recruitment Completion (Providers)

T3 is a time point only relevant to rheumatology providers. No action is needed from participants at T3.

The following forms will be completed at T3:

- Provider Survey: This survey will be given to rheumatology providers with one or more patients enrolled in the research study. This survey asks providers about their experience with the study as well as information related to encounters with patients enrolled in the study.

Providers will be emailed this survey to complete through a REDCap link. Emails with the REDCap link to the survey will be sent out 2 weeks after our final participant completes their T2 survey. Providers will **NOT** be informed of which of their patients participated in the study. Study personnel will follow up with providers once a week via email to complete the survey a maximum of three times.

G3f. T4: 3 Months Post-Intervention

T4 will begin for participants 3 months post-intervention.

The following forms will be completed at T4:

- 3 Month Survey: This survey asks participants about any potential pregnancies post-intervention, their current birth control habits, and their knowledge on pregnancy risks in the context of rheumatic disease.

Participants will be emailed this survey via a REDCap link (as described in REDCap instructions section). Prior to emailing, study personnel will call participants to remind them of their upcoming survey. Study personnel will follow up with participants once a week via email and phone to complete the survey for a maximum of three times.

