[Prompt] Were those conversations different at all after using MyVoice:RD?

- Do you feel confident in your ability to get answers to your reproductive health question? Seek out reproductive health care?

[Prompt] Did MyVoice:RD help at all?

N. Statistical Analysis Plan

Measures

We collected baseline information about participants' demographic and personal characteristics. Questions about contraception use, reproductive histories, and healthcare utilization were adapted from the National Survey of Growth. The Desire to Avoid Pregnancy scale was used to assess patients' preferences around a future pregnancy.

Feasibility, usability, and acceptability of MyVoice:Rheum and the control pamphlet were assessed using qualitative and quantitative measures. The validated Intervention Appropriateness Measure (IAM) and Acceptability of Intervention Measure (AIM) consist of Likert scales ranging from 1-5; we assigned a feasibility threshold of ≥ 3.5 of 5 for AIM and IAM scores, for which higher scores indicate more positive responses. Usability was assessed via summary scores from the System Usability Scale (SUS), which consists of a 10-item Likert scale with scores ranging from 0-100; we set a threshold of scores >80.3 as 'A'/excellent and 68-80.3 as 'B'/very good, consistent with standard rating for the SUS. To assess the perceived value of MyVoice:Rheum and the pamphlet, we developed a five-item Likert scale with responses ranging from 1-5 (1: strongly disagree, 5: strongly agree).

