While pilot studies are not designed to test hypotheses, we preliminarily assessed the effectiveness of MyVoice:Rheum in prompting family planning discussions by comparing the incidence in which these discussions occurred across the study arms. We also evaluated self-efficacy and knowledge scores within each arm before and after the intervention. Self-reported efficacy in communicating with providers was assessed using a modified version of the validated five-item Perceived Efficacy in Patient-Provider Interactions (PEPPI) scale. Rheumatology-specific reproductive health knowledge was assessed via ReproKnow, a measure developed and preliminarily validated by our team that covers domains of contraception safety and efficacy, pregnancy management, pre-conception planning, medication safety, fertility; a score of nine indicates the highest level of reproductive knowledge. Overall knowledge scores as well as scores related to specific domains of reproductive knowledge were calculated across individuals in each study arm. Among MyVoice:Rheum users only, knowledge was assessed again three months after the intervention.

Analysis

Quantitative. Quantitative measures of demographics, feasibility, and acceptability were assessed via descriptive statistics. Among MyVoice:Rheum users and controls, we conducted paired comparisons pre- and post-intervention regarding self-efficacy and reproductive health knowledge, using McNemar's test for proportions and Wilcoxon's signed rank test for means. Calculations were performed using Stata 17.0.

Qualitative. A deductive approach was used to prepare the preliminary codebook, which was organized by the following domains: feasibility and acceptability; family planning discussed at rheumatology visit (yes/no), and reasons why or why not; barriers and facilitators to discussing family planning at the rheumatology visit; ideal timepoints and contexts to use the tool; and suggested modifications. Interview transcripts were entered into NVivo software to

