Three-month outcomes. Most MyVoice:Rheum users engaged in interviews three months following the intervention (N=30). Some MyVoice:Rheum users indicated receipt of family planning services after the intervention, including: 1) initiation of a new birth control method (N=7); 2) counseling about birth control or pregnancy planning from a clinician (N=4); and/or 3) a clinic visit or medical test related to birth control or pregnancy planning (N=3). When reproductive knowledge was re-evaluated again three months, overall scores remained significantly higher than pre-intervention scores (pre-intervention mean 5.77 (SD 1.76) vs. post-intervention 7.27 (1.17), mean difference 1.50 (1.93)).

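### The protocol schedules three-month follow-up for both arms, but three-month knowledge and service receipt are given for MyVoice users only, without explanation, so the service counts are uncontrolled

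*Combined protocol and SAP*

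**What the plan says.** **Protocol, T4 schedule.** Sections G2f (telemedicine) and G3f (clinic) both state "T4 will begin for participants 3 months post-intervention". Neither limits the survey, the interview or the chart extraction to one arm.

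**Protocol, content.** Section C lists, under "T4: 3 Month Survey", four instruments: the "National Survey of Family Growth Family Planning Services Question", PEPPI, ReproKnow and the London Measure of Unintended Pregnancy. The same services question is also listed at T0. Chart data on contraception orders, counselling codes, referrals and related items are collected "within 24 hours of their rheumatology visit, and again 90 days later at T4".

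**SAP, Measures.** On baseline content: "Questions about contraception use, reproductive histories, and healthcare utilization were adapted from the National Survey of Growth". On three-month knowledge: "Among MyVoice:Rheum users only, knowledge was assessed again three months after the intervention". Neither Measures nor Analysis specifies a three-month analysis of service receipt for either arm.

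**Results, Three-month outcomes.** "Some MyVoice:Rheum users indicated receipt of family planning services after the intervention": 7 started a new contraceptive method, 4 were counselled by a clinician, and 3 had a related visit or test. The text reports 30 MyVoice users interviewed and gives no control number.

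**The concern.** A randomised control arm was followed under a schedule that covers it, yet at three months it disappears from the report. A reader cannot tell whether control data were collected and left out, or whether T4 was not carried out in that arm.

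This matters because services listed as received after the intervention are easily read as services received because of it. Over two-thirds of the sample already used contraception, so some method changes and counselling could occur without the tool. The documents give no background rate. The SAP says effectiveness was preliminarily assessed, and the pilot is meant to inform a later trial. A one-arm count could therefore be carried forward as a signal it cannot support.

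**Working it through.** No sample size, power or alpha is stated, so there is no design figure to reproduce. The check compares the schedule with the report and then sizes the counts.

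**1. Schedule against report**

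| T4 item | Scheduled for | Reported for | T0 value shown beside it |
|---|---|---|---|
| ReproKnow | participants, no arm limit | MyVoice only | yes, pre-intervention mean |
| Services question or service receipt | participants, no arm limit | MyVoice only | no, though scheduled at T0 |
| PEPPI | participants, no arm limit | not reported at T4 | not applicable |
| 90-day chart extraction | participants, no arm limit | no separate chart result | not applicable; first extraction follows the visit |

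The missing arm limit does not look like loose drafting. Where the protocol means one arm, as for time with the tool at T1 (G2c, G3c), it names that arm.

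**2. Size of the counts**

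Inputs: 7, 4 and 3 from Three-month outcomes. The denominator of 30 interviewed is an assumption, because the text does not say whether the counts come from interview, survey or chart. Exact (Clopper-Pearson) 95% limits are the 0.025 quantile of Beta(x, n−x+1) and the 0.975 quantile of Beta(x+1, n−x).

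- New method: 7/30 = 23.3% (9.9 to 42.3)
- Counselling: 4/30 = 13.3% (3.8 to 30.7)
- Visit or test: 3/30 = 10.0% (2.1 to 26.5)

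With all 31 MyVoice completers as denominator the proportions are 22.6%, 12.9% and 9.7%, so this choice matters little.

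**3. What a control arm could add**

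Nine controls completed the study. No control T4 count is given, so the control counts below are assumed. Newcombe limits for the difference d = p1 − p2, with Wilson limits (l, u) for each arm, are d − √[(p1−l1)² + (u2−p2)²] and d + √[(u1−p1)² + (p2−l2)²].

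For 7/30 the Wilson limits are 0.118 and 0.409; for 2/9 they are 0.063 and 0.547. Then d = 0.233 − 0.222 = 0.011, the lower limit is 0.011 − √(0.115² + 0.325²) = −0.334, and the upper limit is 0.011 + √(0.176² + 0.159²) = 0.248.

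| Assumed controls | Difference, points | 95% CI |
|---|---|---|
| 0/9 | +23.3 | −8.7 to +40.9 |
| 2/9 | +1.1 | −33.4 to +24.8 |
| 4/9 | −21.1 | −52.2 to +9.9 |
| 0/12 (planned arm size) | +23.3 | −3.5 to +40.9 |

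Every interval includes zero, even with no control events.

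**4. Three-month knowledge**

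Quantitative Outcomes gives pre-test 5.77 (SD 1.76), post-test 7.27 (1.17) and difference 1.50 (1.93). Three-month outcomes gives the same six numbers. The subtraction is consistent (7.27 − 5.77 = 1.50), but no distinct three-month value is shown even for MyVoice.

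**The case against.** The best defence is that T4 is peripheral. Section J2 calls it supplementary, the Recruitment Plan puts all non-exploratory outcomes on one day, and service receipt is not a listed endpoint. The results describe the counts in temporal terms, without a test or a claim of effect, and the SAP says pilots are not meant to test hypotheses. The only interview guide supplied is about MyVoice, which could explain interviewing that arm alone. All of this stands and limits the weight of the point. None of it explains MyVoice-only ReproKnow or services items, or the absence of control chart data, which need no survey response.

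Several stronger readings are tempting but unsupported:

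- **That service use has no baseline.** The services question is scheduled at T0, and the SAP's baseline paragraph covers contraception and healthcare use. What is missing is a baseline count beside the three-month counts. The largest count is also already described as new methods.
- **That the SAP methods limit service receipt to MyVoice.** They limit knowledge only; the restriction on services appears in the results.
- **That control data were collected and dropped.** The SAP sentence is in the past tense, and its plain reading is that control knowledge was not assessed at three months. The documents do not settle this.
- **That T4 was due from every randomised woman.** The protocol provides for withdrawal.

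**Conclusion.** The mismatch between protocol and report is real and unexplained. As reported, the 7, 4 and 3 counts are uncontrolled, lack a baseline comparison, and support no inference about MyVoice.

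A reader might go further and infer that control data would show the counts are not due to MyVoice. They would not: with about 9 controls the interval spans roughly 50 to 62 points across the assumed counts, so an effect could be neither established nor excluded. The percentages rest on 30 as denominator, and the differences rest on assumed control counts; the mismatch itself rests on neither.

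Severity is modest, because T4 is supplementary and the study is a pilot. It is still worth correcting, since it changes what the three-month results can be said to show.

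**What to change.** 1. State whether T4 survey and 90-day chart data were collected for controls, and how many women were reached at T4 in each arm.
2. If they were collected, remove the MyVoice-only restriction. Report T4 ReproKnow, PEPPI, the services item and chart-extracted services for both randomised arms, descriptively and with denominators. Place the T0 survey values alongside. The first chart extraction follows the visit, so it should not be presented as a pre-intervention baseline.
3. If they were not collected, keep the SAP sentence, record the departure from G2f/G3f with its reason, and label the 7, 4 and 3 counts as uncontrolled, with no inference about MyVoice.
4. In either case, give the source and denominator of those counts and report or account for T4 PEPPI. Reconcile the three-month knowledge figures with the immediate post-test figures.

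The cost is a sentence or two and, if the data exist, one table. If control charts were not extracted, recovering them would take staff time and depend on the HIPAA authorisations. The price is a very imprecise and possibly less favourable comparison.

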MyVoice is a web-based patient-centered decision aid developed to help women with rheumatic diseases make informed decisions about pregnancy and other family planning decisions. This pilot trial is designed to assess the extent to which MyVoice decision aid can be feasibly and acceptably implemented into the rheumatology clinical setting and will inform operational procedures for a future hybrid effectiveness-implementation trial. Women in the intervention arm will receive the MyVoice decision aid (n=38). Women in the control arm (n=12) will receive a paper-based version of the American College of Rheumatology pamphlet about pregnancy, which, similarly to MyVoice, targets women with a broad range of rheumatic diseases.

[figure not shown]
B. Protocol Summary

| | |
|---|---|
| Title: | A Pilot Study to Assess Feasibility and Acceptability of MyVoice, a Family Planning Decision Aid for Women with Rheumatic Diseases |
| Grant Number: | K23 AR075057-01A1 |
| Study Description: | This protocol describes procedures and goals for the pilot testing of MyVoice, a web-based decision aid to help women with autoimmune diseases clarify their reproductive goals and learn about if and how their autoimmune diseases and medications affect these goals. Primary hypothesis: MyVoice will be feasible and acceptable to patients who receive rheumatology care. |
| Objectives* : | Our aim is to conduct a pilot trial to assess feasibility and acceptability of MyVoice vs. a patient pamphlet among female patients ages 18-44 (n=55) who receive rheumatology care. |

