Participants will be emailed this survey via a REDCap link (as described in REDCap instructions section). Prior to emailing, study personnel will call participants to remind them of their upcoming survey. Study personnel will follow up with participants once a week via email to complete the survey for a maximum of three times.

Participants will also complete a follow-up interview at the T4 time point. Research coordinators will reach out to participants 3 months post-intervention to schedule the interview. Coordinators will reach out to schedule interview once a week via email and phone to complete the survey for a maximum of three times.

Research coordinators will collect the following PHI from electronic health records at T4:

- Orders for pregnancy tests (urine, serum)
- Orders for emergency contraception
- Billing code for family planning or contraception counseling
- Order for non-emergency contraception method
- Order/Referral for obstetrics-gynecology or maternal-fetal medicine consultation
- Order/Referral for PCP consultation for family planning indication
- Prescription for prenatal vitamin
- Change from fetotoxic/teratogenic disease-modifying anti-rheumatic drug or small molecule medication to a pregnancy-compatible anti-rheumatic drug
- Documentation of pregnancy

G3. Clinic Participants

Clinic participants will be asked to arrive to their rheumatology clinic visits 1 hour early to complete required study activities. Research coordinators will meet with participants in an available space in the clinic. If space is not available, study activities will be completed outside (weather permitting) or in a neutral space inside.

G3a. Consent

Consent will occur prior to performing any of the research interventions/interactions and before the participant goes to their clinic appointment. At consent, a research coordinator will walk through the informed consent document with participants and answer any questions that arise. If the participant agrees to participate, both the participant and the research coordinator will sign the informed consent document. They will also sign a HIPAA authorization allowing study personnel to access their medical records.

G3b. T0: Baseline

The following forms are to be completed at T0:

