facilitate coding and thematic analysis. Transcripts were reviewed by two experienced qualitative analysts with master's degrees in public health and sociology, respectively ([name], [name]). [name] and [name] used an open coding approach to identify themes that arose inductively, and subsequently refined the codebook based on the most frequent and important codes. [name], a trained research assistant, also independently coded the transcripts. As a form of investigator triangulation, the analysts and P.I. ([name]) used a consensus approach to reconcile coding and create new codes. Focus coding was used to re-review all transcripts and synthesize themes.

RESULTS

Sample Characteristics

Fifty-five patients consented to participate in the study, among whom 46 patients were randomized to a study arm. Forty patients completed the study, among whom 31 patients were randomized to the MyVoice:Rheum intervention and 9 were randomized to the control arm. The most common rheumatic disease diagnoses were SLE, RA, and myositis. Most participants identified as heterosexual, and nearly half of all participants were married. More than half of participants had at least a college degree. Over 40% of participants identified their rheumatologist as their main health provider. Most participants had never been pregnant, and approximately 10% had a diagnosis of infertility. Over two-thirds of participants used a method of contraception.

Quantitative Outcomes

MyVoice:Rheum and the control pamphlet were both rated as feasible, acceptable, usable, and valuable by study participants. The minimum threshold score of 3.5 for the Acceptability of Intervention Measure (AIM) was met or exceeded by 96.8% of MyVoice:Rheum users and 88.9% of controls; average AIM scores for MyVoice:Rheum and controls were 4.4 (S.D. 0.58) and 3.97 (S.D. 0.65), respectively. The minimum threshold score of 3.5 for the Intervention Appropriateness Measure (IAM) was met or exceeded by 96.8% of MyVoice:Rheum users and 88.% of controls; average IAM scores among MyVoice:Rheum and controls were 4.48 (S.D. 0.60) and 4.11 (S.D. 0.85), respectively. System Usability Scale scores for MyVoice:Rheum users were rated in the range of "excellent", whereas scores for pamphlet users were rated in the range of "very good" (83.0 vs. 79.3, respectively).

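### For PEPPI and ReproKnow the SAP specifies only within-arm pre-post tests and defines no MyVoice-minus-pamphlet difference or interval, so the reported gains cannot be read as effects over the pamphlet

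*Combined protocol and SAP*

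**What the plan says.** Section C lists PEPPI and ReproKnow in both the T0 Baseline Survey and the T2 Exit Survey, with no restriction by arm. Section I (G1) randomises patients to MyVoice or the pamphlet by sealed envelope.

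Section N, Measures, says of these scores: "We also evaluated self-efficacy and knowledge scores within each arm before and after the intervention". Section N, Analysis (Quantitative), says: "Among MyVoice:Rheum users and controls, we conducted paired comparisons pre- and post-intervention regarding self-efficacy and reproductive health knowledge". The tests it names, McNemar and Wilcoxon signed rank, are both paired. Measures adds that overall and domain knowledge scores were calculated for each arm, which is a summary and not a contrast. The one between-arm effectiveness comparison in the SAP concerns family planning discussions: "comparing the incidence in which these discussions occurred across the study arms".

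The objective in Section B is to "conduct a pilot trial to assess feasibility and acceptability of MyVoice vs. a patient pamphlet". Neither PEPPI nor ReproKnow is in the Section B endpoint list.

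On numbers, the Results state: "Fifty-five patients consented to participate in the study, among whom 46 patients were randomized to a study arm". They continue: "Forty patients completed the study, among whom 31 patients were randomized to the MyVoice:Rheum intervention and 9 were randomized to the control arm".

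On the three-month time point, Section N, Measures, says: "Among MyVoice:Rheum users only, knowledge was assessed again three months after the intervention". Section C includes ReproKnow in the T4 survey, and Section I (G2f and G3f) sends that survey to participants without naming an arm: "Participants will be emailed this survey via a REDCap link".

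**The concern.** Between T0 and T2 every participant answers the same questionnaires a second time, sees her rheumatologist, and has been given educational material of one kind or the other. A rise within the MyVoice arm contains all three influences as well as anything specific to the tool. Randomisation is the design feature that separates them, and it does so only through a comparison between arms. A paired test within each arm does not make that comparison.

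The pilot is meant to inform a later hybrid effectiveness-implementation trial, so gains of 0.59 and 1.50 may be carried forward as if they measured what MyVoice adds. The SAP defines no difference or interval that would tell a reader how far they do.

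Two related matters affect the three-month knowledge result. The schedule and the SAP disagree on who was assessed, and the figures reported at three months are the same as those reported at post-test.

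**Working it through.** **1. Which comparison is defined**

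| Outcome | Collected in both arms? | Analysis in Section N |
|---|---|---|
| Family planning discussion | Yes | Incidence compared between arms |
| ReproKnow, T0 and T2 | Yes (Section C) | Calculated in each arm; paired test within each arm |
| PEPPI, T0 and T2 | Yes (Section C) | Paired test within each arm |

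The SAP's own paired tests in controls presuppose control scores at both times.

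**2. Reported changes (Results, Quantitative Outcomes)**

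- PEPPI, MyVoice users: 3.47 (SD 1.19) to 4.07 (0.82), stated change 0.59 (0.91). Check: 4.07 − 3.47 = 0.60, which agrees up to rounding.
- ReproKnow: 5.77 (1.76) to 7.27 (1.17), stated change 1.50 (1.93). Check: 7.27 − 5.77 = 1.50. The paragraph on three-month outcomes presents these values as those of MyVoice users.

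No control values for either score appear in the text, so the between-arm estimate itself cannot be computed. Its expected precision can.

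**3. Precision of a baseline-adjusted T2 difference, 31 vs 9**

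Assumptions: control SDs equal the MyVoice SDs, all completers have both scores, and the ReproKnow figures above are the T2 values.

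Pre-post correlation, r = (SD₁² + SD₂² − SD_d²) / (2·SD₁·SD₂):

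- ReproKnow: (3.0976 + 1.3689 − 3.7249) / 4.1184 = 0.180
- PEPPI: (1.4161 + 0.6724 − 0.8281) / 1.9516 = 0.646

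Residual SD = SD₂·√(1 − r²):

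- ReproKnow: 1.17 × √(1 − 0.180²) = 1.151
- PEPPI: 0.82 × √(1 − 0.646²) = 0.626

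Ordinary half-width = t(0.975; 37) × residual SD × √(1/31 + 1/9), with t = 2.026 and the root = 0.3786:

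- ReproKnow: 2.026 × 1.151 × 0.3786 = 0.88
- PEPPI: 2.026 × 0.626 × 0.3786 = 0.48

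Simulating the regression of T2 score on arm and T0 score (3,000 trials per case) gives the mean HC3 half-width:

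| Case | ReproKnow | PEPPI |
|---|---|---|
| Control SDs equal to MyVoice SDs | ±0.94 | ±0.51 |
| Control post-test SD stays at the pre-test value | ±1.24 to ±1.31 | ±0.70 to ±0.76 |

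In the equal-SD case these are 0.94/1.50 = 63% and 0.51/0.59 = 86% of the reported gains. Across the cases simulated, coverage of the nominal 95% interval was 0.94 to 0.96 with HC3 and 0.87 to 0.95 with the ordinary standard error. The shortfall arises when the small arm has the larger spread.

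Simpler estimators are no narrower than the ordinary adjusted interval under equal SDs. An unadjusted T2 difference gives ±0.90 and ±0.63, and a difference in change scores gives ±1.48 and ±0.70.

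**4. Three-month figures**

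| | Pre | Post | Change |
|---|---|---|---|
| Quantitative Outcomes (post-test) | 5.77 (1.76) | 7.27 (1.17) | 1.50 (1.93) |
| Three-month outcomes | 5.77 (1.76) | 7.27 (1.17) | 1.50 (1.93) |

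All six values agree to the last digit, including the SD of the change.

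**5. Numbers analysed**

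46 randomised − 40 completed = 6 not completing (6/46 = 13%). The Results do not give their arm, nor the n behind each score.

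**The case against.** The strongest reply is that the documents never say MyVoice beat the pamphlet on either score. They report rises within the MyVoice group, and the SAP says openly that scores were evaluated within arms. The SAP also states that pilots are not designed to test hypotheses, Section F says there is no sample size calculation, and the objective concerns feasibility and acceptability, for which the Results do give figures in each arm. All of this stands, and it limits the point to interpretation. It does not remove it: the SAP still applies significance tests within arms, and the three-month paragraph still makes a significance claim. A pilot's limits favour an estimate with an interval over within-arm tests.

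A second reply is that ReproKnow scores are already planned by arm, so a crude difference follows by subtraction. That is correct for ReproKnow and narrows the gap, but subtraction supplies no interval, and PEPPI has no equivalent sentence.

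A third is that nine controls are too few. That is a reason to show the width. Baseline adjustment with HC3 is one reasonable choice, and a simple difference with its interval would also answer the point.

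A reader might go further in three ways that the documents do not support:

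- **That control results were withheld.** An exhibit may be missing from the text available, so this cannot be inferred.
- **That the between-arm result would be less favourable than the within-arm gains.** No control values are shown, so its direction is unknown.
- **That the duplicated figures show which time point is wrong.** They show only that the two need checking.

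**Conclusion.** The point holds for two exploratory scores and for how they are interpreted. It does not touch the feasibility and acceptability conclusions. PEPPI and ReproKnow were scheduled before and after in both randomised arms, yet the SAP defines no between-arm difference or interval for either. The gains of 0.59 and 1.50 should therefore not be read as effects of MyVoice over the pamphlet.

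A between-arm estimate from the existing data would be imprecise: about ±0.94 ReproKnow points and ±0.51 PEPPI points with HC3 (±0.88 and ±0.48 with the ordinary standard error). These widths depend on control SDs that the documents do not give. They widen if control SDs are larger, and the ReproKnow figure also assumes that the duplicated numbers are the T2 values.

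The identical ReproKnow figures are a separate reporting defect. Until they are checked, the claim that three-month scores were significantly above baseline is unsupported. The protocol and SAP also disagree on whether controls were assessed at T4.

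**What to change.** 1. Report T0 and T2 PEPPI and ReproKnow scores by arm, with n per arm and per score. Define the population as randomised participants with both scores, and give the arm of the 6 who did not complete.
2. Add the MyVoice-minus-pamphlet T2 difference from a linear regression of T2 score on arm and T0 score, with a 95% CI using HC3 standard errors. Label it exploratory and post hoc, and make no significance claim.
3. Keep within-arm changes as description only.
4. Check the post-test and three-month ReproKnow figures, and their n, against source data before keeping the significance statement.
5. Reconcile the T4 schedule in Sections C and I with the SAP's restriction to MyVoice users. If no control T4 data exist, say so and label the three-month result single-arm and uncontrolled.

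The cost is SAP wording, one by-arm table, two regressions on data the schedule already collects, and one data check. The drawback is a wide interval with 9 controls.
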